4.1 Overall Design

We will determine the feasibility of conducting a randomized controlled trial of tight blood pressure control (<135/85 mmHg on home BP monitoring) vs. standard of care (<150/100 mmHg on home BP monitoring) in postpartum individuals following a HDP with assessment of individuals who are eligible, enrolled, and remain in the study until six weeks postpartum. We will further assess individuals who are retained in the study for 6 months postpartum. Lastly, we will analyze our effect outcomes to inform the sample size for a subsequent large-scale randomized trial. This will be done through analysis of mean arterial pressure (MAP), systolic

blood pressure, and diastolic blood pressure of participants at 6 weeks and at 6 months postpartum.

The study will be conducted on the postpartum unit of Magee-Womens Hospital. Participants will be enrolled at the time of postpartum hospitalization with study visit #1 occurring in the hospital. At this study visit, participants will be administered questionnaires, will provide a blood sample, and BP will be measured. Study visit #2 will be a remote study visit conducted via telemedicine or a telephone call at 6 weeks postpartum. At this visit, participants will provide questionnaires and blood pressure data. Study visit #3 will be a remote study visit conducted via telemedicine or a telephone call at 6 months postpartum. At this visit, participants will again provide questionnaires and blood pressure data. The study overview is depicted below.

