5.3 Strategies for Recruitment and Retention

Recruitment: We will recruit 60 individuals with preeclampsia or gestational hypertension from the MWH postpartum units, using recruitment methods effectively employed by our team previously. There are approximately 100 eligible individuals per month (~1200 per year).

We plan to recruit women from the post-delivery unit with the appropriate diagnoses. Upon review of a potential subject's chart to determine eligibility, the study coordinator will flag the chart for potential eligibility. The potential participant will first be approached by the study physician or a member of the clinical care team directly caring for her to ask about her willingness to be approached for participation in a research study. If the potential participant indicated willingness to be approached, then the research team will be contacted and the potential subject will be screened regarding enrollment.

Retention: Participants will receive monetary compensation which will be distributed amongst their study visits. We propose monetary compensation of \$125 total with \$25 distributed at enrollment, \$25 distributed at the first study visit, and \$25 distributed at the second study visit and \$50 at the final study visit.

Randomization and blinding: We will randomize consented participants into two arms: tight BP control (<135/85 mmHg) vs. usual care in 1:1 at the individual level. A randomization sequence using permuted block randomization with randomly varying block sizes will be generated by RedCap. This will be a pragmatic, non-masked trial. At randomization, treating physicians will be notified of their patient's participation and randomization group.

6 Study Intervention

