8.1 Efficacy Assessments

Feasibility outcomes: As listed in Table, will include enrollment, randomization, retention.

Blood pressure measurement: Mean arterial pressure (mmHg) at six weeks and six months postpartum will be assessed at a remote research study visit. MAP is defined as the average BP during one cardiac cycle and will be calculated

as $MAP = SBP + 2(DBP)/3$. BP will be measured in all women in a standardized manner by trained research staff using the same validated device as at the enrollment visit. Due to diurnal variations in BP, we will attempt to schedule all study visits between 8-10am consistent with clinical guidelines. If this cannot be performed due to participant scheduling limitations, we will ensure that BP is measured at a consistent time of the day across all visits. Following a 5-minute rest, BP will be measured in triplicate on the non-dominant arm with one-minute intervals using an appropriately sized cuff. These measures will be directly observed by research study staff.

Table. Feasibility outcomes		
Feasibility outcome	Descriptive statistic	Feasibility target
Identification of participants	mean, SD, 95% CI	Review 50 medical records per month to assess for eligibility
Screening	mean, SD, 95% CI	Average screening rate of 8-10 participants/month
Enrollment	mean, SD, 95% CI	Average enrollment rate of 4-5 participants/month
Randomization	n, %, 95% CI	>80% of enrolled participants
Retention to 6 months postpartum	n, %, 95% CI	>80% of randomized participants
Study measures consistency	n, %, 95% CI	>90% of randomized participants
Acceptability	n, %, 95% CI	>80% of randomized participants based on survey questionnaires

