Secondary outcomes are systolic and diastolic BP, and chronic hypertension at 1-year postpartum (stage 1 or stage 2) derived from office BP in women randomized to tight control compared to women to receiving usual care. We will also compare the use of anti-hypertensive agents across the study period, quantitatively assessed using the therapeutic intensity score [TIS], which is a summary measure that accounts for the number of medications and the relative doses received, which will be summarized across the study period and compared by randomization arm. As an exploratory analysis, we will quantitatively simulate BP based on confounding effects of anti-hypertensive medications using published metrics of the lowering effect of various anti-hypertensive agents. Finally, we will evaluate care utilization across study arms, including postpartum readmission and Emergency Room visits

Questionnaires: The participant will complete questionnaires about demographics, medical history, obstetric and gynecologic history, physical activity, mood, diet, breastfeeding, sleep, and overall health and support. At subsequent visits, the participant will also answer questions about the intervention.

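### Follow-up BP is described as staff-measured and directly observed, yet visits 2 and 3 may be telephone calls; for any such call the MAP outcome would be an unverified self-report in an open trial

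*Combined protocol and SAP*

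**What the plan says.** Section 4.1 (Overall Design) sets the mode of both follow-up visits: "Study visit #2 will be a remote study visit conducted via telemedicine or a telephone call at 6 weeks postpartum" and "Study visit #3 will be a remote study visit conducted via telemedicine or a telephone call at 6 months postpartum". On who supplies the 6-week readings it says: "At this visit, participants will provide questionnaires and blood pressure data". The 6-month visit is described in the same way.

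Section 8.1 (Efficacy Assessments) agrees that the setting is remote: "Mean arterial pressure (mmHg) at six weeks and six months postpartum will be assessed at a remote research study visit". The same paragraph then says that "BP will be measured in all women in a standardized manner by trained research staff using the same validated device" as at enrollment, a visit that Section 4.1 places in hospital. It specifies triplicate readings after a rest and adds: "These measures will be directly observed by research study staff".

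Two other places point to in-person measurement. Later in Section 8.1 the chronic hypertension outcome is "derived from office BP in women randomized to tight control", and Section 7.3 speaks of participants not returning to the clinic.

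On masking, Section 5.3 states: "This will be a pragmatic, non-masked trial". Section 6.3 repeats this.

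**The concern.** Staff who are not in the room cannot take a cuff reading, and on a telephone call they cannot see one being taken. Where a visit is by telephone, the systolic and diastolic values behind MAP would be numbers that the participant reads out. The trial is open and home BP is titrated to an arm-specific target for the first six weeks, so she probably knows what number is wanted. Rounding toward the target, or repeating until a reading looks good, could then differ between arms and favour tight control.

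The primary feasibility outcomes are untouched. What is at stake is the use made of MAP. It is the only outcome with a power statement, it carries the preliminary efficacy test in Section 9.2, and Sections 1.1, 3 and 4.1 use the BP outcomes to size the next trial. A reporting bias would pass into both.

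**Working it through.** **1. The text.** Three questions, with the answers the plan gives:

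| Question | Section 4.1 | Section 8.1 |
|---|---|---|
| Where? | Remote, video or telephone not fixed | Remote for MAP; office for chronic hypertension |
| Who takes the reading? | Participant provides it | Trained research staff |
| How is it verified? | Not stated | Direct observation by staff |

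Video could satisfy the observation requirement, though the participant and not the staff would still be taking the reading. A telephone call satisfies neither requirement. The plan does not say that video is required, that the enrollment device goes home, or how a spoken reading is checked.

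**2. The plan's own power figure.** Inputs from Section 9.2: SD 8 mmHg, 48 analysed (24 per arm with 1:1 allocation), type I error 20%, difference 5 mmHg, stated power 80%.

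- SE = 8 × √(2/24) = 2.31 mmHg.
- Two-sided, noncentral t with 46 df: power 80.7% (normal approximation 81.2%).
- One-sided, normal approximation: 90.7%.

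The stated 80% therefore matches a two-sided 20% test, which is used below.

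**3. What a differential reporting shift would do.** The documents give no figure for this, so the shift *b* is an assumption, shown as a range. It is the net displacement of the between-arm difference in mean MAP toward tight control, with no true effect. The noncentrality is b / 2.31 and the critical t is 1.300.

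| b (mmHg) | b / SE | Any rejection | Rejection favouring tight control |
|---|---|---|---|
| 0 | 0 | 20% | 10% |
| 1 | 0.43 | 24.1% | 19.7% |
| 2 | 0.87 | 35.2% | 33.6% |
| 3 | 1.30 | 50.7% | 50.2% |

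**4. How large a shift per reading this needs.** If a share *p* of tight-control readings is affected by an average *s* mmHg, and usual care is unaffected, then b = p × s. For b = 2, s is 2 mmHg at p = 100%, 4 at p = 50% and 8 at p = 25%. The plan gives no value for p.

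**5. Effect on planning.** Required sample size varies as 1/difference². If the pilot showed 5 mmHg of which 1 was reporting, the true difference would be 4, and the next trial would need (5/4)² = 1.56 times the number planned.

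**6. Cost of discarding unverified readings.** The power calculation of step 2 (noncentral t), repeated with smaller arms, gives 80.7% at 24 per arm, 79.4% at 23 and 78.0% at 22. Losing one reading per arm already takes the test just below the stated 80%.

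**The case against.** Section 8.1 puts remote visits and direct observation in one paragraph, so it evidently intends observed remote readings, and video telemedicine could deliver them. A reader might infer that the whole MAP outcome will be self-reported. The documents do not support that: it follows only for telephone visits, whose number is unknown.

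A reader might also infer that participants are coached toward a number. No section says so. Notification of arm is stated only for treating physicians (Sections 5.3 and 6.3), and Section 6.1.1 adds that monitoring nurses are unblinded. That participants know their arm and target is a fair inference from an open trial with home titration, but it remains an inference.

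The larger shifts may be too pessimistic. Reading the Section 8.1 formula as (SBP + 2 × DBP)/3, 135/85 is a MAP of 305/3 = 101.7. With the Section 9.2 mean of 94 and SD of 8, about 17% of women would exceed it on a normal approximation. If only they shaded readings, a 2 mmHg shift in the arm mean would need 2/0.17 ≈ 12 mmHg each, and 3 mmHg about 18. If 30% shaded, the figures are about 7 and 10. This is rough, since more women could exceed 85 diastolic alone, but it is a fair reason to treat the table as illustration.

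The mechanism is also weaker at 6 months, because Sections 1.1 and 6.1.1 describe six weeks of monitoring (Section 4.2 speaks of six months). Section 9.4.1 makes hypothesis testing secondary to estimation, and Section 9.2 sends any positive result to a confirmatory trial.

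These points limit the size and reach of the problem. They do not remove the contradiction, and a confirmatory trial does not protect against a planning difference that was biased when it was chosen.

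**Conclusion.** The conflict is real, lies in current text, and is not resolved elsewhere. For every telephone visit, the plan's own measurement standard cannot be met and MAP would be an unverified self-report.

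The consequence is conditional on three things the documents do not give: the share of telephone visits, how far participants are aware of their target, and any differential shift in reporting. Its direction, toward tight control, is plausible but not shown. If the net shift were 1 mmHg, overall rejection under no effect would move only from 20% to 24%, but false results favouring tight control would nearly double, from 10% to 20%. At 2 and 3 mmHg that one-directional figure is 34% and 50%. These rest on 24 per arm, SD 8 and a two-sided 20% test.

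This should be corrected before outcome data accrue, because the change is cheap and the MAP estimate feeds the next trial. It does not threaten the primary feasibility objective.

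**What to change.** Reconcile Sections 4.1 and 8.1, including the office BP wording, so that they give one account of who takes follow-up BP, with which device, in which setting and how it is verified:

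- At visits 2 and 3 the participant takes the triplicate reading on a specified validated device while research staff observe by video.
- If video is not possible, obtain all of the device's stored, time-stamped readings for the visit window. Photographs chosen by the participant do not serve, because they leave her free to repeat and select.
- Record visit mode and verification status for each visit, and report both by arm.
- Repeat the MAP comparison excluding unverified readings, as a prespecified sensitivity analysis.
- Keep unverified telephone readings in the main analysis, flagged. Discarding them would cost power, as step 6 of the working shows.

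The cost is protocol wording, two fields on the visit form, some added visit logistics, and a slightly smaller verified sample in the sensitivity analysis. The fallback assumes a device with time-stamped memory, which the documents do not confirm. The verification record could also support the study measures consistency target (above 90%) in the Section 8.1 feasibility table. No treatment rule changes.

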8.2 Safety and Other Assessments

Answering Questionnaires: There is a possibility of emotional discomfort associated with answering the questionnaire as some of the questions may be considered “personal” and answering them might be stressful or embarrassing. Participants may skip questions for which they feel uncomfortable.

Risks of the Tight Control Intervention Program: For some women, there may be a small but present risk of hypotension, meaning your blood pressure goes too low. If this occurs, it may cause symptoms such as dizziness, shortness of breath, palpitations, light-headedness, and/or falls. We advise women who are experiencing these symptoms to immediately contact their health-care provider and to avoid carrying their newborn due to risk of falls. Additionally, we will monitor rates of breastfeeding continuation given the theoretical risk for decreased milk supply.

9 Statistical Considerations

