1.1 Synopsis

Title: Feasibility of tight control versus usual postpartum care following hypertensive disorders of pregnancy: a randomized controlled trial

Study Description:

Objectives:

- Primary Objective: To assess the feasibility of conducting a randomized controlled trial of tight blood pressure control (<135/85 mmHg on home blood pressure monitoring) vs. standard of care (<150/100 mmHg on home blood pressure monitoring) in postpartum individuals following a hypertensive disorder of pregnancy (HDP).
- Secondary Objectives: To assess the effect of tight blood pressure control on longer-term blood pressure control and postpartum care utilization to inform sample size for a subsequent large-scale randomized trial

Endpoints:	Primary Endpoint:	Proportions of individuals who are eligible, enroll, and remain in the study through 6 weeks postpartum (Target: >40% enrollment, >80% retention)
	Secondary Endpoints:	Mean arterial blood pressure, systolic blood pressure, and diastolic blood pressure at 6 weeks and 6 months postpartum at a research study visit. Proportion with stage 1 or greater hypertension at each study visit. Mean home blood pressures throughout first six weeks postpartum. Care utilization including postpartum emergency room visits, hospital readmissions, and outpatient office visits.

Study Population:

Phase:	3
Description of Sites/Facilities Enrolling Participants:	Single-center, tertiary care center
Description of Study Intervention:	Tight blood pressure control defined as goal home blood pressure <135/85 via remote blood pressure monitoring for 6 weeks postpartum
Study Duration:	6 months

Participant 6 months
Duration:

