2.1 Study Rationale

There are inconsistent clinical recommendations for management of postpartum hypertension. There is overwhelming evidence of benefit of lower BP targets in a non-pregnant population and in individuals with chronic hypertension in pregnancy.^{22,23} Specifically for non-pregnant individuals, the American College of Cardiology (ACC) recommended BP threshold for initiation of an antihypertensive medication is 140/90 mmHg and even lower, 130/80 mmHg, for individuals at high risk for CVD. Recently, the Chronic Hypertension and Pregnancy (CHAP) trial found benefit in targeting a BP threshold of 140/90 mmHg for initiation of medications during pregnancy for individuals with chronic hypertension.²² Despite this, ACOG continues to recommend a threshold of 150/100 mmHg for initiation of anti-hypertensive medications in the postpartum period.⁹ This approach fails to consider the anticipated exacerbation of hypertension and is likely a contributor to hypertension-related maternal morbidity and mortality in the postpartum period.²⁴ Despite the inconsistent management recommendations, professional societies (including ACOG, ACC and Society for Maternal Fetal Medicine) recognize the public health significance and the need for a well-designed trial to evaluate the benefits and harms of tighter blood pressure control in the postpartum period.^{9,27,28}

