2.3 Risk/Benefit Assessment

2.3.1 Known Potential Risks

- Symptomatic hypotension
- Possible decrease in breastmilk supply impacting breastfeeding continuation

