6.1 Study Intervention(s) Administration

6.1.1 Study Intervention Description

Following hospital discharge, individuals with HDP are enrolled in a clinical home BP management program and are prompted, via a secure text message to report their BP for the first six weeks postpartum. This program is overseen by Drs. [name] and [name]. Remote monitoring nurses will be unblinded to treatment arm and will follow study protocols for enrolled participants based on study arm.

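### Symptomatic hypotension is a named risk of tight control, but no hypotension outcome is defined, specifically asked about, or planned for comparison by arm

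*Combined protocol and SAP*

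**What the plan says.** Section 2.3.1 lists two known potential risks. The first is "Symptomatic hypotension" and the second is a possible fall in milk supply. Section 8.2 discusses both under the risks of the tight-control programme. For hypotension it lists symptoms, including dizziness and falls, and then gives advice: "We advise women who are experiencing these symptoms to immediately contact their health-care provider". For milk supply it commits to a measurement: "we will monitor rates of breastfeeding continuation given the theoretical risk for decreased milk supply".

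The outcome lists are in the synopsis (1.1), the objectives table (Section 3), the feasibility table and secondary outcomes (8.1), and the analysis text (9.4.2 and 9.4.3). They cover feasibility, clinic-type and home blood pressure, hypertension status, medication intensity and care utilization. Hypotension, its symptoms and falls appear in none of them. Home blood pressure is listed as "Mean home blood pressures throughout first six weeks postpartum".

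Several data streams could carry relevant information:

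- In the remote programme, women are "prompted, via a secure text message to report their BP for the first six weeks postpartum" (6.1.1).
- Section 8.1 adds: "At subsequent visits, the participant will also answer questions about the intervention".
- Acceptability questions cover perceived harms (9.4.2).
- Emergency visits and readmissions are evaluated across arms (8.1).

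**The concern.** The tight arm starts and adjusts treatment at a lower blood pressure than usual care, so hypotension is the harm most directly tied to the contrast under test. Section 9.2 says the pilot exists to gather planning information for a larger trial, and Section 2.1 reports that professional societies see "the need for a well-designed trial to evaluate the benefits and harms of tighter blood pressure control in the postpartum period". The plan gives blood pressure and medication intensity a comparison by arm but gives hypotension none.

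This matters for two reasons. Usual-care women also receive antihypertensives, at a higher threshold (6.1.2), so hypotension noted in the tight arm alone cannot show an excess. The trial is also unmasked, and the monitoring nurses know the arm and follow arm-specific protocols (6.1.1, 6.3). If symptoms are recorded only when someone happens to raise them, reporting could differ between arms for reasons unrelated to the true rate. Dizziness or a fall that nobody asked about cannot be reliably recovered later.

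**Working it through.** **Step 1. Compare the two named risks.** Milk supply has a stated measure (breastfeeding continuation, 8.2) and a questionnaire topic (8.1). Hypotension has a symptom description and advice. The document gives it no definition, blood pressure cut-off, event log or symptom item. Adverse events otherwise appear only as a possible reason for withdrawal (7.2).

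**Step 2. Check each existing channel.**

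| Channel | Section | Reaches both arms? | Specified to capture hypotension? |
|---|---|---|---|
| Texted home readings, six weeks | 6.1.1, 1.1 | Yes | No; summarised as a mean, which can hide low values |
| Questions about the intervention at later visits | 8.1 | Not limited to one arm in the text | No; content not stated |
| Perceived harms within acceptability | 9.4.2 | Not limited to one arm in the text | No; semi-structured and open-ended, not an event count |
| Emergency visits and readmissions | 8.1 | Yes | No; misses events that do not lead to hospital care |

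**Step 3. Check the reporting commitment.** Section 9.4.1 promises estimates with 95% CIs, overall and by arm, for feasibility and efficacy outcomes. Safety outcomes are not mentioned.

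**Step 4. Reproduce the plan's precision figure.** Section 9.2 gives a within-arm 95% margin of error of at most 0.18 with 30 per arm. The worst case is p = 0.5: 1.96 × √(0.25/30) = 0.179, which agrees. With 24 per arm it is 1.96 × √(0.25/24) = 0.200.

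**Step 5. What a solicited hypotension outcome could show.** Section 9.2 assumes 80% retention, 0.80 × 60 = 48, or 24 per arm if losses are even. With zero events, the exact two-sided 95% upper limit is 1 − 0.025^(1/n):

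- n = 30: 1 − 0.025^(1/30) = 0.116
- n = 24: 1 − 0.025^(1/24) = 0.142

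Items asked at visits 2 and 3 reach only retained women, so the 24-per-arm figure is the relevant one for them.

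The document gives no hypotension rate, so the rates below are assumptions. The chance of at least one event in an arm is 1 − (1 − p)^n:

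| Assumed rate p | n = 24 | n = 30 |
|---|---|---|
| 2% | 38% | 45% |
| 5% | 71% | 79% |
| 10% | 92% | 96% |

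**Step 6. Could it be a powered comparison?** No. For assumed rates of 5% and 15% with 30 per arm, the 95% half-width of the difference is 1.96 × √(0.05×0.95/30 + 0.15×0.85/30) = 0.150, wider than the 10-point difference itself. Power at two-sided 5% is about 25% (normal approximation) or 9% (Fisher's exact test). Even for 5% and 30%, power is about 73% or 63%. The use is estimation.

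**The case against.** The strongest reply is that this is a 60-woman feasibility pilot. Evaluating harms is what the societies cited in Section 2.1 ask of the field; it is not an objective set for this study, and any hypotension comparison would be descriptive. That is correct, and it limits the weight of the point. It does not remove it, because the plan already runs a preliminary efficacy comparison to inform the next trial.

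A reader might also infer more than the document supports:

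- **That hypotension becomes known only if a woman calls her provider.** The advice in 8.2 tells a symptomatic woman how to protect herself; it is not presented as the way the study collects data. Home readings, later questionnaires and perceived-harms questions are other possible routes. What is missing is a specification that any of them captures hypotension.
- **That the trial cannot compare harm between arms.** Breastfeeding continuation is monitored, and emergency visits and readmissions are evaluated by arm. The gap concerns hypotension, not all harm.
- **That reporting will be biased by a known amount.** Lack of masking and arm-specific nurse protocols make unequal reporting plausible, but the document gives no capture rates, so its direction and size cannot be computed.

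Finally, the Schedule of Activities (1.3) and Safety Analyses (9.4.4) show headings without text in the version available, and relevant text may have been lost. The point therefore rests on the outcome lists and on 9.4.1.

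**Conclusion.** The point holds in its limited form: hypotension is a named risk, but it is not defined, specifically solicited, or planned for comparison by arm. Incidental information would exist, but not a systematic rate in each arm. The consequence is lost planning information; the feasibility outcomes and the mean arterial pressure comparison are unaffected.

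What could be gained is modest: with zero events in an arm, a rate above 11.6% (30 women) or 14.2% (24 women) would lie outside the 95% interval. These limits assume that every woman counted was actually asked or had usable readings, and the 24 assumes 80% retention spread evenly. The conclusion also assumes that no safety outcome is set out in the sections whose text is not visible. The change is worth making because it is cheap and unasked symptoms are hard to recover afterwards.

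**What to change.** 1. At visits 2 and 3, ask every woman in both arms the same fixed items on hypotension symptoms and falls since the last visit, within the existing questionnaires.
2. From the home readings already collected, report by arm the number of women with low readings, using a cut-off set in advance by the clinical investigators. Show the number of readings submitted per woman beside it, since more readings give more chances of a low one.
3. List these two outcomes, with the breastfeeding continuation already monitored, as safety outcomes in Sections 1.1, 3 and 8.1.
4. Under 9.4.4, state that counts, denominators and risk differences with 95% CIs will be given by arm as descriptive results, with no hypothesis test. Use an exact or score-type interval, because counts may be near zero.

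The cost is a few questionnaire items and one descriptive table; no new visit or device is needed. The downside is that asking about symptoms raises the background count in both arms, since dizziness or light-headedness may have other causes. Identical wording and timing in both arms keeps the comparison fair in that respect, although answers in an unmasked trial can still be influenced by knowledge of the arm.
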